### **3.4.2 Treatments Administered**

Dosing will begin with 10-µg mRNA-1325 or placebo (Cohort 2), followed by 25-µg mRNA-1325 or placebo (Cohort 3), and then 100-µg mRNA-1325 or placebo (Cohort 4). The rationale for dose selection is described in [Section 1.5](#). Dosing cohorts will advance as described in [Section 3.4.2.1](#).

Vaccine will be administered as an IM injection (0.5 mL) into the deltoid muscle as a 2-dose vaccination schedule at Visits 1 and 4 (at least a 28-day interval between dosing). The second dose of study drug will be administered preferably in the same arm used for the first dose.

The clinic will be appropriately staffed, trained on emergency resuscitation, and have stocked available rescue medications (such as epinephrine, steroids, antihistamines, and IV fluids) should any severe reaction (eg, anaphylaxis or profound urticaria) occur that requires immediate intervention.

#### **3.4.2.1 Dose Escalation**

##### **Internal Safety Team**

An IST will oversee the safety of the trial and will review blinded safety data during Part A of the study to ensure adherence to the protocol, monitor safety laboratory test results and reactogenicity, and raise concerns to the SMC should there be safety issues or operational challenges that could affect subject safety. Pause rules have been pre-established to trigger ad hoc SMC reviews, if required ([Section 3.4.2.2](#)), and the IST will review (blinded review) safety

laboratory test results, vital sign measurements, reactogenicity, and any AEs (all with toxicity scoring/grading) during the active vaccination phase of the trial. In addition, recruitment rates, timing of vaccination sequence, and window adherence will be reported to the IST. The chairperson of the IST may request that additional data be provided to the SMC that relates to the safety of subjects (eg, study conduct, quality issues, or safety concerns).

At minimum, the IST will be composed of the Sponsor's study medical monitor lead, the contract research organization's medical monitor, and the principal investigator(s). The medical monitor will oversee safety aspects of the study and will participate as needed. Additional ad hoc members may be included as needed.

### **Safety Monitoring Committee**

The SMC will review data for dose escalation when at least 90% of subjects dosed (eg,  $\geq 27$  out of 30 subjects) in Cohort 2 (10- $\mu$ g mRNA-1325 or placebo) have safety data inclusive of their visit 7 days following the second vaccination (Visit 5). Once a recommendation is given by the SMC, the Sponsor will approve advancing to Cohort 3 (25- $\mu$ g mRNA-1325 or placebo). Cohort 4 (100- $\mu$ g mRNA-1325 or placebo) will be randomized following SMC review and Sponsor approval of Cohort 3 (data inclusive of 7 days following the second vaccination of  $\geq 90\%$  of subjects dosed [eg,  $\geq 27$  out of 30 subjects]).

To allow cohort advancement, the following data from the highest dosed cohort is expected to be reviewed by the SMC: 1) toxicity scoring of safety laboratory test results through 7 days following the second vaccination (through Visit 5); 2) toxicity scoring of vital sign measurements and reactogenicity through 7 days following the first and second vaccination (through Visit 5); 3) all unsolicited AEs (with grading and relatedness). Data will be prepared by dose category and timing relative to last vaccination. As safety data on all cohorts accumulate, the SMC will include in their review ongoing AEs as well as cumulative safety laboratory test results, reactogenicity, and AEs across vaccine doses as long as subjects remain in Part A of the study, thereby providing a cumulative review of safety. Should a cohort pause occur due to pre-specified criteria ([Section 3.4.2.2](#)), the SMC will be convened for an unscheduled (ad hoc) meeting and receive specific safety data related to the trigger of the pause.

The SMC may recommend advancement to the next dosing cohort, request additional information prior to providing a recommendation, recommend stopping the study, recommend changes to study conduct and/or the protocol, or recommend additional operational

considerations due to safety issues that arise during study conduct. The Sponsor has the authority to accept (or amend) the SMC recommendations, to stop the study at any time, to request a cohort pause for safety concerns (to be addressed by the SMC), and to request additional consultation during study conduct for either safety concerns or operational issues. The SMC will also be convened should a pause rule be triggered or at the request of the IST, the investigator(s), or the Sponsor.

The SMC will be comprised of 3 voting and independent members who are medical doctors familiar with Phase 1 clinical trial and safety review and independent from the trial. In addition, a biostatistician not associated with the trial will prepare the safety data (non-voting member), and a coordinator not associated with the trial will organize and record decisions of the SMC (non-voting member). The SMC may decide to include a non-medical person to weigh in on ethical issues if the need arises.

### **3.4.2.2 Pause Rules**

During the active vaccination period, if any of the following events occur and are assessed to be potentially mRNA-1325 related, the cohort will be paused for further enrollment and vaccination, and an unscheduled SMC will be convened to assess specific data concerns and make recommendations:

- Two or more Grade 3 (or greater) reactogenicity events (whether systemic or local) within a dose cohort following any single (eg, the first, the second) vaccination
- Two or more Grade 3 (or greater) same laboratory toxicity score within a dose cohort
- One or more SAEs assessed as vaccine related, including any systemic hypersensitivity reaction

An unscheduled SMC may also be convened (with vaccination pausing if deemed necessary), by the investigator, IST, or Sponsor, if any other significant safety or tolerability issues are identified in the comprehensive review of available data that warrant further evaluation before additional subjects are dosed. This may include emerging non-clinical data, clinically relevant AEs, or relevant data from other sources indicating safety concerns even if the event(s) per se does not meet the criteria specified in this section.

Should a pause be triggered in the study, then each subject's visits will continue until the next scheduled vaccination visit. Should a pause affect a subject's vaccination visit, then the window for that subject's vaccination visit will be suspended until the pause is lifted and vaccination can resume. Once the pause is lifted at the site, vaccination should be reinstated as soon as possible. Visits should thereafter be scheduled as if they had received their second vaccination within the 28 (+7) day time window.

Should a pause be prolonged such that the second vaccination takes place outside the 28 (+7) day time window, the Sponsor has the option to add additional subjects in a dosing cohort to achieve the original number of subjects planned to be dosed within the 28 (+7) day time window. If a subject is in the screening period for more than 28 days as the result of a pause, they may be rescreened for study eligibility as long as they continue to provide consent to participate in the study.

Dosing adjustments may be made during the conduct of the study should the data reveal the need to adjust dosing due to the observed immune response or a change in the perceived benefit:risk ratio. However, treatment assignment will not be released to the subjects or to those individuals involved in managing or assessing safety in Part B of the study until Part B of the study is completed.

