## 1.5 Rationale for Dose Selection

Dosing will begin with 10 µg (Cohort 2), followed by 25 µg (Cohort 3), and then 100 µg (Cohort 4). There will be no Cohort 1 included in this study. The 10 µg dose was chosen as a starting dose based on both pre-clinical data with mRNA-1325 and clinical data from two Phase 1 trials with different mRNAs in the same formulation as mRNA-1325. The pre-clinical no-observed-adverse-effect level (NOAEL) was established as 50 µg for repeated IM dosing in the rat. This supports the starting dose of 10 µg in this study.

In an ongoing clinical study with the Moderna mRNA H10N8 influenza vaccine, which utilizes the same the lipid composition as mRNA-1325, the tolerability profile of the vaccine administered according to a 2-dose vaccination schedule in a dose range of 25 µg to 100 µg

was acceptable, and the vaccine induced a robust immune response. According to Bahl and colleagues (Bahl et al 2017), the majority of solicited AEs reported in the 100- $\mu$ g group were mild (107/163 events; 66%) or moderate (52/163 events; 32%). The majority of events were injection site pain, myalgia, headache, fatigue, and chills/common-cold-like symptoms. Only 4 events (2.5%), reported by 3 subjects, were categorized as severe and included injection site erythema (1.2%), injection site induration (0.6%), and chills/common cold (0.6%). No related SAEs occurred in the study.

In order to inform dose choices in this study, Moderna performed a group unblinding analysis of immunogenicity data from the first dose cohort (ie, Cohort 2: 10  $\mu$ g of mRNA-1325). The analysis confirmed that the vaccine is able to induce neutralizing antibodies against Zika virus in both flavivirus-seronegative and flavivirus-seropositive subjects. Following review of the immunogenicity results from this cohort and considering the variability of the serological assay and the biological variability of the immune response, Moderna decided to increase the dose for Cohort 4 from 50  $\mu$ g to 100  $\mu$ g.

Available non-clinical and clinical data support the starting dose in this study of 10  $\mu$ g and a maximum dose of 100  $\mu$ g.

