### **3.3 Withdrawal of Subjects From the Study**

#### **3.3.1 Reasons for Withdrawal**

Subjects can withdraw consent and discontinue from the study at any time, for any reason, without prejudice to further treatment.

The investigator can also withdraw a subject, upon the request of Moderna Therapeutics, Inc. or if Moderna Therapeutics, Inc. terminates the study. Upon occurrence of a serious or intolerable AE, the investigator will confer with the Sponsor or designee. If a subject desires to withdraw from the study because of an AE, the investigator will try to obtain agreement to continue to follow that subject for that event only until it is resolved or until stable and then complete an EOS form. In the event of a safety concern that results in withholding from further vaccination, the subject will be continued in the trial for safety evaluations.

Every reasonable attempt will be made to follow subjects for safety throughout the entire trial period even if further vaccination is withheld or the subject misses visits. The reason for subject withdrawal or lost to follow-up will be documented.

The investigator, in consultation with the Sponsor's medical monitor, **may** withhold a subject **from further vaccination** if the subject experiences any of the following:

1. Becomes pregnant;
2. Develops, during the course of the study, symptoms or conditions listed in the exclusion criteria;

3. Experiences an AE (other than reactogenicity) after vaccination that is considered by the investigator to be possibly or probably related to treatment and is of Grade 3 (severe) or higher severity;
4. Experiences an AE or SAE that, in the judgment of the investigator, requires study drug withdrawal due to its nature, severity, or required treatment, regardless of the causal relationship to treatment;
5. Experiences a clinically significant change in clinical laboratory test results, vital signs, or general condition that, in the judgment of the investigator, requires treatment withdrawal;
6. Experiences anaphylaxis clearly attributed to study vaccine;
7. Experiences generalized urticaria related to the study vaccine.

The reason for withdrawing or refusing from further vaccination will be recorded. In addition, if a subject refused further vaccination they will be continued in the trial with all planned visits and assessments relative to the vaccination schedule and including visits through 1 year post final vaccination.

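### Chills is neither solicited nor graded, so related, non-serious Grade 3 chills cannot by itself count toward the mandatory cohort pause or prompt the 24-hour call (minor; cheap to improve)

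*Protocol*

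**What the plan says.** **Mandatory pause.** Section 3.4.2.2 pauses a cohort for potentially related events of three kinds. The first is "Two or more Grade 3 (or greater) reactogenicity events (whether systemic or local) within a dose cohort" following any single vaccination. The second is two or more of the same Grade 3 laboratory score. The third is one or more vaccine-related SAEs.

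**What counts as reactogenicity.** Section 3.5.6 defines it as selected signs and symptoms recorded on the memory aid. The systemic list is temperature, myalgia, arthralgia, headache, fatigue/malaise, nausea/vomiting and diarrhea. Table 6-3 grades the same items. The instruction to contact the clinic within 24 hours depends on a Grade 3 reactogenicity score.

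**Unsolicited events.** Section 3.5.7.4 makes an unsolicited AE Grade 3 only if it prevents daily activity and also requires medical intervention.

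**Prior evidence.** Section 1.5 cites an influenza mRNA vaccine with the same lipid composition. After giving the 100 µg figures it states: "The majority of events were injection site pain, myalgia, headache, fatigue, and chills/common-cold-like symptoms". Chills/common cold accounts for one of the four severe events.

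**Other safeguards.** Section 3.1 requires the internal safety team (IST) to review reactogenicity, laboratory results and AEs through Day 7 in three sentinel vaccinees before the rest of a cohort is randomized. The SMC sees all unsolicited AEs before escalation. Section 3.4.2.2 adds a discretionary route for other concerns: "An unscheduled SMC may also be convened (with vaccination pausing if deemed necessary").

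**The concern.** The trial takes its top dose from a dataset in which chills/common cold was a solicited event, and then leaves chills off its own solicited list without giving a reason. Because the pause rule and the 24-hour call are both built on that list, the omission carries into safety monitoring.

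The trial is first-in-human, and Cohort 4 receives the 100 µg dose of the cited group. Without the 24-hour call, severe chills may first be reported at the reminder call (about Day 4, Table 6-1 footnote n) or at the Day 7 (+3) visit, while other members of the cohort are still being dosed. Chills that keeps a subject from daily activity but needs no medical care would not be graded 3 at all, although fatigue or myalgia of the same severity would be.

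**Working it through.** **1. The plan's own figures (Section 1.5, 163 solicited events at 100 µg).** 107/163 = 65.6%, 52/163 = 31.9%, 4/163 = 2.45%, and 107 + 52 + 4 = 163. The severe events are erythema 2/163 = 1.2%, induration 1/163 = 0.6% and chills/common cold 1/163 = 0.6%, so 2 + 1 + 1 = 4. All agree with the text. These are shares of events; no per-subject chills rate is given.

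**2. Tracing one case.** Take related, non-serious Grade 3 chills in one vaccinee.

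- Trigger 1: not met, because chills is not on the Section 3.5.6 list.
- Trigger 2: not met, because chills is not a laboratory score.
- Trigger 3: not met, because the case is not serious.
- 24-hour call: not prompted, because there is no reactogenicity score.

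The same holds for any number of such cases.

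**3. Illustration on assumed rates.** Each cohort has 24 vaccinees (Section 3.1). The other inputs are assumptions:

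- c: chance per dose of related, non-serious chills that would be Grade 3 on the fatigue/myalgia wording. Under Section 3.5.7.4 the rate can only be the same or lower.
- o: share of those subjects who also have one listed Grade 3 reaction.
- b: chance per dose that any other vaccinee has one listed Grade 3 reaction.

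Per dose, K ~ Bin(24, c), I ~ Bin(K, o), J ~ Bin(24 − K, b), and x = P(K ≥ 2 and I + J ≤ 1). Treating the two doses as independent, the chance of at least one such occurrence is 1 − (1 − x)². At c = 2%, o = 0, b = 0: x = 0.0826 and 1 − 0.9174² = 15.8%.

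| o | b | c = 1% | 2% | 3% | 5% |
|---|---|---|---|---|---|
| 0 (upper bound) | 0 | 4.7% | 15.8% | 29.6% | 56.3% |
| 50% | 0 | 3.5% | 11.4% | 21.0% | 39.0% |
| 80% | 0 | 1.6% | 5.3% | 9.5% | 17.2% |
| 100% | 0 | 0 | 0 | 0 | 0 |
| 50% | 2% | 2.6% | 8.5% | 15.7% | 29.6% |
| 80% | 2% | 1.1% | 3.6% | 6.5% | 11.8% |

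**4. Subjects with several listed events.** Trigger 1 counts events, so one vaccinee with Grade 3 fever and Grade 3 fatigue meets it alone. Suppose one third of subjects with a listed reaction have two or more. With b = 2%, the o = 50% row becomes 1.9/6.5/12.1/22.9% and the o = 80% row 0.8/2.5/4.6/8.3%. If all of them have two or more, the o = 80% row becomes 0.1/0.4/0.7/1.2%.

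**5. Sentinel review.** The chance of at least one case among three sentinels after dose 1 is 1 − (1 − c)³. That is 1 − 0.98³ = 5.9% at c = 2% and 1 − 0.95³ = 14.3% at c = 5%.

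**6. Effect of the fix.** With chills solicited, the chance that chills alone meets the two-event rule among 24 vaccinees after one vaccination is P(K ≥ 2): 8.3% at c = 2% and 33.9% at c = 5%. As written it is 0 at any rate.

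**The case against.** **The discretionary routes are real.** The IST reviews all graded AEs during active vaccination, and the SMC will be convened if the IST, an investigator or the Sponsor asks. The Sponsor may request a pause, and data are due within three business days (Section 3.7). Chills is therefore monitored, and the sentinel review is a mandatory step that covers it. This stands and is why the point is minor. It does not close the gap: the sentinel step rests on three subjects after dose 1, the escalation review protects the next cohort, and Cohort 4 has no later escalation.

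**The evidence is thin.** There is one severe event under a composite label. A reader might infer that the cited study shows a pause that this rule would have missed. It does not. Its three severe local events, spread over two doses, put at least two after one dose, so trigger 1 would probably have fired without chills, provided that severe means Grade 3 and the events were judged related.

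**The solicited list is a legitimate choice.** It follows the cited grading scales and contradicts nothing in the protocol. That is accepted; the point is an improvement, not an error.

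**Section 3.3.1.** A reader might see a mismatch with its listed ground "Experiences an AE (other than reactogenicity) after vaccination that is considered by the investigator" to be related and Grade 3 or higher. The documents do not support that. The investigator may withhold further vaccination on that ground, and the SMC may be convened for other AEs; both are discretionary.

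**Conclusion.** The point holds as a minor, cheap improvement. On the text alone, related, non-serious Grade 3 chills cannot by itself count toward the mandatory pause or prompt the 24-hour call. After the sentinel review, a within-cohort pause for it rests on referral by the investigator, IST or Sponsor, unless a listed Grade 3 reaction or a related SAE also occurs.

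The probabilities depend on assumed values of c, o and b and on independence between subjects and doses; the protocol supplies none of these. The 56.3% figure should not be read as an estimate: it needs a 5% rate and no overlap with fever, fatigue or myalgia. Overlap and multiple listed events per subject pull the figures down, to about 1% or less across the whole range of c in the most favorable non-zero case shown.

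**What to change.** For cohorts not yet dosed, add chills to the memory aid, the Section 3.5.6 systemic list and Table 6-3. Grade it like fatigue and myalgia, with Grade 3 meaning significant and preventing daily activity, and not like arthralgia, which also needs medical intervention. Trigger 1 and the 24-hour call then apply with no change to the pause rule's wording.

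Summarize solicited chills only for the cohorts in which it was solicited, against those cohorts' own placebo recipients. This is an exception to the pooling of placebo across cohorts in Section 3.6.5.

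Optionally, add a pause trigger for two or more subjects in a cohort with a related Grade 3 or greater unsolicited AE of the same preferred term. It would not fully cover unsolicited chills, because Section 3.5.7.4 still requires medical intervention for Grade 3.

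**Cost.** One list line, one table row, one memory-aid and eCRF row, and an amendment with IRB approval (Section 5.2.1). There are no extra visits or samples, and the chance of a pause rises slightly. Ascertainment would be uneven. Section 1.5 reports a "group unblinding analysis of immunogenicity data from the first dose cohort", so Cohort 2 has already been dosed and there would be no solicited chills data at 10 µg. Of 3 × 24 = 72 planned vaccinees and 3 × 6 = 18 planned placebo recipients, at most 48 and 12 would be covered, or 24 and 6 if only Cohort 4 remains.

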### **3.4.7 Treatment Compliance**

All doses of study drug will be administered at the study site under direct observation of study site personnel and appropriately recorded (date and time) in the eCRF. Site personnel will confirm that the subject has received the entire dose of study drug. If a subject does not receive study drug or does not receive all of the planned doses, the reason for the missed dose will be recorded.

Subjects that miss the second vaccination due to noncompliance with the visit schedule and not due to a cohort pause will still be required to follow the original visit and testing schedule. These subjects will be asked to undergo blood collection to comply with a second immune test at Visit 7 (56+7 days after first vaccination).

The study site is responsible for ensuring subjects comply with the study windows allowed. Should a subject miss a visit, every effort will be made to contact the subject and achieve a visit within the defined visit window. If a subject exceeds their post-vaccination visit in excess of 28 days from the scheduled visit or misses a vaccination schedule by more than 28 days (eg,

28 days beyond the scheduled time of vaccination), then that visit will be classified as a missed visit and the subject will continue with subsequent visits for Parts A and B of the study. All safety requirements of the missed visit will be captured and included in the follow-up visit (eg, safety laboratory testing, memory aid review for reactogenicity, immune testing, as applicable).

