#### **Part A:**

- Solicited AEs with toxicity scoring (local and systemic reactogenicity events) collected for 7 days following each vaccination
- Unsolicited AEs collected for 28 days following each vaccination; additional classification if serious, medically attended, leading to study withdrawal, or an AESI
- Safety laboratory test results with toxicity scoring (hematology, serum chemistry, and coagulation) collected at Baseline and 7 (+3) days and 28 (+7) days following each vaccination
- Urinalysis test results with toxicity scoring collected at Baseline and 7 (+3) days following each vaccination

- A subset of safety laboratory test results (as specified in [Table 6-1](#)) with toxicity scoring collected additionally at 17 ( $\pm 3$ ) days following each vaccination and 21 (+3) days (sentinel subjects) following the first vaccination
- Vital sign measurements with toxicity scoring on day of vaccination and 7 and 28 days following each vaccination

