**Part A:**

- Neutralizing serum antibody titers (PRNT50) to Zika (Baseline [pre-vaccination at Visit 1] and at 28 days following each vaccination [Visits 4 and 7, respectively])
- Neutralizing serum antibody titers (PRNT50) to yellow fever (Baseline [pre-vaccination at Visit 1] and at 28 days following each vaccination [Visits 4 and 7, respectively]) in the flavivirus-seropositive group
- T-cell response (cytokine activation to IFN $\gamma$  or other cytokines) (Baseline [pre-vaccination at Visit 1] and at 7 days following each vaccination [Visits 2 and 5, respectively]), if results of interim immunogenicity analyses warrant further analyses of samples.

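### A cohort pause suspends the whole of Visit 4, not only the second injection, so the Day 28 post-dose-1 titer and safety assessments can be taken late

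*Protocol*

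**What the plan says.** Section 3.4.2.2 opens by saying what a pause stops: "the cohort will be paused for further enrollment and vaccination". Assessments are not mentioned. The same section then sets the operating rule:

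- Each subject's "visits will continue until the next scheduled vaccination visit".
- If the pause catches that visit, its window "will be suspended until the pause is lifted and vaccination can resume". No maximum is given there.
- After the pause, "Visits should thereafter be scheduled as if they had received their second vaccination within the 28 (+7) day time window".

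Visit 4 has two functions. It is the dose-2 visit. In Table 6-1 it is also the Day 28 (+7) visit after dose 1, carrying the pre-dose PRNT50 and exploratory samples, full safety labs, urinalysis, vital signs, examination, unsolicited AE review and memory aid collection.

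The endpoints rest on that visit. Section 3.6.2 defines the Zika titer endpoint, and the yellow fever titer in seropositive subjects, as measured "at 28 days following each vaccination [Visits 4 and 7, respectively"]. Section 3.6.1 lists safety labs "collected at Baseline and 7 (+3) days and 28 (+7) days following each vaccination" among the primary endpoints, and also vital signs 28 days after each vaccination.

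Sections 3.1 and 3.4.7 have a rule that holds subjects to the original visits and tests when dose 2 does not happen, but its opening words exclude pauses: "Subjects that miss the second vaccination due to noncompliance with the visit schedule and not due to a cohort pause will still be required".

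**The concern.** The rule ties an assessment to an injection. Once the injection is on hold, the text postpones the Day 28 blood draw and safety visit with it, although nothing about the assessment needs the injection.

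The titer matters more. Visit 4 is the only scheduled post-dose-1 PRNT50 time point, so there is no neighbouring sample to fall back on. Each dose level is a single cohort, so a pause in one cohort shifts sampling time for that dose and not for the others. A difference in post-dose-1 titer between doses would then mix the effect of dose with time since vaccination. The secondary objective is to select a dose from these titers, and Section 3.6.7 says the cohort-by-cohort results inform dose decisions.

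On safety, the main case is a cohort that has just met a pause criterion. For affected subjects, the next scheduled clinic assessment after Day 17 (Day 21 for sentinels) would wait for vaccination to resume. The analysis plan cannot repair this, because a sample not drawn at Day 28 cannot be recovered later.

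**Working it through.** The plan states no figure that depends on this rule (Section 3.6.3 reports no formal sample size calculation), so there is nothing to reproduce. The check is a reading of the visit rules followed by day arithmetic.

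**Which provisions could keep Visit 4 on time**

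| Provision | Keeps the Day 28 assessment on schedule? |
|---|---|
| 3.4.2.2, opening: pauses enrollment and vaccination | Suggests so, but does not mention assessments |
| 3.4.2.2, operating rule: visits run up to the vaccination visit, whose window is then suspended | No |
| 3.4.2.2, after the pause: visits are timed from the delayed dose 2 | No make-up Day 28 visit |
| 3.1 and 3.4.7, original-schedule rule | Excludes cohort pauses |
| 3.4.7, missed-visit rule (more than 28 days late) | Collects the content at the follow-up visit, so late |
| 3.5, unscheduled visits | Allowed, not required |

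**When the assessment becomes late**

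Inputs: Visit 4 window Day 28 to 28 + 7 = 35 (Table 6-1). Let a pause begin *s* days after a subject's dose 1, before Visit 4 has taken place, and last *L* days. Both are assumptions.

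- Earliest day for Visit 4 = max(28, *s* + *L*).
- It is out of window if *s* + *L* > 35.
- A pause starting on Day 7 can last 35 − 7 = 28 days without harm to that subject.
- A pause starting on Day 28, when the visit falls due, does harm once it exceeds 35 − 28 = 7 days.

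For a subject whose Visit 4 is due on the first day of the pause (*s* = 28):

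| Assumed *L* (days) | Earliest Visit 4 | Within Day 28–35? | More than 28 days late? |
|---|---|---|---|
| 7 | Day 35 | yes | no |
| 14 | Day 42 | no | no |
| 21 | Day 49 | no | no |
| 28 | Day 56 | no | no |
| 42 | Day 70 | no | yes |

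In the last row, if the missed-visit rule of 3.4.7 applies to pauses, Visit 4 becomes a missed visit and its content moves to the next one.

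**If the pause is never lifted**

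The original-schedule rule, including its second immune test at Visit 7, excludes these subjects. Table 6-2 has a row for subjects without dose 2, and it starts at Day 84 after dose 1. Section 3.3.1 keeps a subject withheld from vaccination for safety under follow-up, but gives no visit days.

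**How likely a trigger is (scale only)**

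One trigger is two Grade 3 or greater reactogenicity events in a cohort after one vaccination, assessed as potentially related. Take 24 active subjects (Section 3.1), count two events as two subjects, and treat all as related. With an assumed per-subject rate *p*, P(at least 2 of 24) = 1 − (1 − *p*)^24 − 24*p*(1 − *p*)^23:

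- *p* = 2%: 8%
- *p* = 5%: 34%
- *p* = 10%: 71%
- *p* = 15%: 89%

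The protocol gives no such rate for mRNA-1325. Section 1.5 reports 4 severe events in 3 subjects at 100 µg of another vaccine with the same lipid composition, but without the number dosed or a split by vaccination, so no rate follows from it.

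**The case against.** The strongest reply is that the gap is narrow and the protocol already softens it.

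- **Safety follow-up goes on.** A reader might infer that safety assessment stops in a paused cohort. It does not. The memory aid covers 28 days after each dose (3.5.2), AEs are followed to resolution (3.5.6), a Day 7 lab of Grade 2 or more must be repeated within 10 days (3.5.8), the IST keeps reviewing data (3.4.2.1), and unscheduled visits are open (3.5). This stands: safety is thinned. None of these provisions supplies a PRNT50 sample.
- **Subjects can be added.** Section 3.4.2.2 lets the sponsor enlarge a cohort when dose 2 falls outside its window, and added subjects could give in-window Visit 4 samples. That is optional and does not restore the samples of those already dosed.
- **The Per-Protocol set filters late draws.** Section 3.6.4 requires blood drawn within the permitted windows. Whether a suspended window counts as permitted is not stated, so late samples could be pooled as Visit 4 or dropped. A reader might infer that post-dose-1 titers cannot be compared at all; the text supports confounding by sampling time, or loss of numbers, but not that.
- **The delay is not open-ended in every reading.** The missed-visit rule in 3.4.7 is not confined to noncompliance and may cap the wait. It still yields a late assessment.
- **A whole cohort is a ceiling.** Thirty affected subjects would need every first dose given before the trigger and no Visit 4 yet done, although sentinels are dosed at least 7 days ahead of the rest. Reactogenicity triggers arise within 7 days of a dose, so a pause triggered after dose 1 may well end before the triggering subjects reach Day 35.

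**Conclusion.** The point holds in a conditional form. Following Section 3.4.2.2 as written, a subject whose Visit 4 falls due in a pause that runs past that subject's Day 35 has the Day 28 titer and safety assessments taken late. If the pause is not lifted, they may not be taken at that time point. Late is the sure outcome; lost is the exception.

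The size cannot be fixed from the protocol. It depends on pause length and on how far the cohort has progressed, and neither is given. The Day 42 to 70 figures assume pauses of 14 to 42 days starting on the day the visit is due; shorter or earlier pauses may do no harm. Active and placebo subjects are affected alike, and a pause can also be called for reasons other than the three listed triggers.

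Visit 7 keeps its timing relative to dose 2, and no power statement depends on this. It is nonetheless worth correcting: the only scheduled post-dose-1 titer and several primary safety measurements hang on it, and the correction is cheap.

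**What to change.** In Section 3.4.2.2, state that:

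1. a pause suspends only the vaccination;
2. the Visit 4 pre-vaccination assessments (PRNT50 and exploratory samples, safety labs, urinalysis, vital signs, examination, AE and memory aid review) are still done at Day 28 (+7) after dose 1 and analysed as Visit 4;
3. any sample taken when vaccination resumes carries a separate label.

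The checks that Table 6-1 already requires before an injection stay with the injection, and the rule on when dosing resumes is untouched.

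Keep the exclusion of cohort pauses in Sections 3.1 and 3.4.7 for subjects whose dose 2 is only delayed. Deleting it outright would fix their Visit 7 at 56 (+7) days after dose 1, against Section 3.4.2.2, which times later visits from the delayed dose. Reconcile those sections with 3.4.2.2 only for subjects who never receive dose 2 because of a pause, so that their remaining visits are stated.

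The cost is protocol wording and one extra visit for affected subjects. If both immunogenicity samples are repeated before the delayed dose, that adds 10 + 10 = 20 mL of blood to the 326 mL in Table 3-1.
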